10.1. Study Population

The study population includes adult patients with recurrent symptomatic paroxysmal atrial fibrillation. The AF classifications that will be used for this study are defined in the 2017 HRS/EHRA/ECAS Expert Consensus Statement on Catheter and Surgical Ablation of Atrial Fibrillation. (Calkins, et al. 2017)

Paroxysmal AF is defined as AF that terminates spontaneously or with intervention within 7 days of onset.

Patients in persistent AF are excluded from the study. Persistent AF is defined as continuous AF that is sustained beyond 7 days.

10.2. Subject Enrollment

Patients will be screened to ensure they meet all of the inclusion criteria and none of the exclusion criteria prior to study enrollment. Institutional Review Board (IRB)/Ethics Committee (EC) and Medtronic approval of this CIP and the Informed Consent Form (ICF) must be obtained prior to enrolling subjects in the study. Subjects are considered enrolled in the study upon signing and dating the ICF. Subjects must provide informed consent (IC) before any study related procedures occur.

10.3. Inclusion Criteria

- A diagnosis of symptomatic paroxysmal AF with the following documentation: (1) physician's note indicating recurrent self-terminating AF or paroxysmal AF; and (2) any ECG documented AF within 6 months prior to enrollment.
- Age 18-80

10.4. Exclusion Criteria

- History of AF treatment with class I or III antiarrhythmic drug, including sotalol, with the intention to prevent an AF recurrence. However, patients pretreated with above AAD for less than 7 days with the intention to convert an AF episode are allowed.
- Prior persistent AF (continuous AF that is sustained >7 days)
- Left atrial diameter greater than 5.0 cm
- Prior left atrial ablation or left atrial surgical procedure
- Presence or likely implant of a permanent pacemaker, biventricular pacemaker, loop recorder, or any type of implantable cardiac defibrillator (with or without biventricular pacing function)
- Presence of any pulmonary vein stents
- Known presence of any pre-existing pulmonary vein stenosis
- Pre-existing hemidiaphragmatic paralysis
- Presence of any cardiac valve prosthesis
- Moderate or severe mitral valve regurgitation or stenosis
- Any cardiac surgery, myocardial infarction, PCI / PTCA or coronary artery stenting which occurred during the 90 day interval preceding the date the subject signed the Informed Consent Form
- Unstable angina
- NYHA class III or IV congestive heart failure and/or known left ventricular ejection fraction (LVEF) less than 45%

- Diagnosis of primary pulmonary hypertension
- Rheumatic heart disease
- Thrombocytosis, thrombocytopenia
- Contraindication to anticoagulation therapy
- Active systemic infection
- Hypertrophic cardiomyopathy
- Cryoglobulinemia
- Known reversible causes of AF, including but not limited to uncontrolled hyperthyroidism, severe obstructive sleep apnea, and acute alcohol toxicity.
- Any cerebral ischemic event (strokes or TIAs) which occurred during the 180 day interval preceding the date the subject signed the Informed Consent Form, or any known unresolved complications from previous stroke/TIA
- Existing thrombus
- Pregnancy
- Patient with life expectancy that makes it unlikely 12 months of follow-up will be completed.
- Current or anticipated participation in any other clinical trial of a drug, device or biologic during the duration of this study not pre-approved by Medtronic
- Patients with contraindications to a Holter monitor
- Unwilling or unable to comply fully with study procedures and follow-up

11. Study Procedures

Prior to performing study related procedures, all sites must have IRB/EC approval as well as documentation from Medtronic of center readiness.

11.1. Schedule of Events

The visit schedule and data collection requirements are summarized in Table 5.

Table 5: Visit Schedule and Data Collection Requirements Summary

| | Baseline | Procedure | Hospital Discharge | 1M | 3M | 6 & 12 M | Unscheduled | Reablation/ Crossover Ablation |
|--|----------|--------------------|--------------------|----|----|----------|-------------|-----------------------------------|
| | | Treatment Arm Only | | | | | | |
| Informed Consent | X | | | | | | | |
| Randomization | X | | | | | | | |
| Inclusion/Exclusion | X | | | | | | | |
| Medical History | X | | | | | | | |
| Physical Exam | X | | | | | | | |
| Pregnancy Screening ¹ | X | | | | | | | |
| Review Medications | X | | X | X | X | X | X | X |
| Review of AF Symptoms | X | | | X | X | X | X | X |
| Collect Health Care Utilization Information | | | | X | X | X | X | X |
| 12 Lead ECG | X | | X | X | X | X | X | |
| EQ-5D & AFEQT | X | | | | | X | | X |
| Trans-thoracic Echocardiogram (TTE) ² | X | | | | | | | |
| Trans-esophageal Echocardiogram (TEE) ³ | | X | | | | | | X |

¹ Required only for female subjects of childbearing potential.

² Only required if data not available from within prior 6 months from consent date.

³ TEE must be performed in all subjects who present to the ablation procedure in atrial fibrillation lasting more than 48 hours in duration (or of an unknown duration). However, the TEE is not required if the subject has adequate systemic anticoagulation that has been maintained for at least 3 weeks prior to presenting to the ablation procedure in AF. TEE must be performed if subjects have a CHA₂DS₂-VASc ≥ 2 and present to the procedure with a sub-therapeutic INR (<2.0) or if the subject has had a significant interruption of NOACs. A significant interruption of NOACs is defined as any missed dose within 21 days prior to the ablation procedure.

| | Baseline | Procedure | Hospital Discharge | 1M | 3M | 6 & 12 M | Unscheduled | Reablation/ Crossover Ablation |
|--|---|--------------------|--------------------|----|----|----------|-------------|-----------------------------------|
| | | Treatment Arm Only | | | | | | |
| Ablation Procedure Data | | X | | | | | | X |
| 24 hour continuous ambulatory ECG monitoring | | | | | | X | | |
| Patient Activated Ambulatory ECG Monitoring ⁴ | | | | | X | | | |
| Adverse Events | X | X | X | X | X | X | X | X |
| Device Deficiencies | As they occur | | | | | | | |
| Study Deviations | As they occur | | | | | | | |
| Chest X-ray (treatment arm only) | If phrenic nerve injury is detected during the procedure, the subject will be evaluated with inspiration/expiration chest x-ray at PHD and all follow-up visits until resolved. | | | | | | | |
| MRI or CT Scan (treatment arm only) | Required only for subjects with suspected PV stenosis. | | | | | | | |

11.1.1. Modes of Data Collection

Multiple modes of data collection may be employed to support the collection of required visit data at the 3 and 6 month visits. This includes such methods as:

- In-office patient clinic visit
- Direct to patient contact (i.e. telephone, email, mail contact, etc.)
- Remote technology transmissions/uploads

11.2. Medications

Information regarding drugs prescribed to treat atrial arrhythmias will be collected, including the purpose for their use/reason for modification, and start and stop dates. Information regarding anticoagulation medications will be collected, including start and stop dates.

Control Arm (AAD): Subjects must initiate a Class I or III AAD within 30 days of randomization. It is recommended that AADs be initiated as soon as possible after randomization, with a target of within 14 days. The investigator should choose the appropriate AAD per his or her standard of care; however, amiodarone should only be used if other AADs were not tolerated or failed. The 2014 AHA/ACC/HRS

⁴ Subjects shall submit ECG transmissions weekly and whenever symptoms occur after the AAD optimization/post-ablation blanking periods through 12 month follow-up.

Guideline for the Management of Patients with AF should be consulted for AAD prescriptions. Modifications to AADs (type or dosage increase) may be made for up to 90 days after AAD initiation. This is referred to as the AAD optimization period. Dosing of AADs can be individually tailored until the end of the AAD optimization period. After the optimization period, further AAD therapy optimization or change should be avoided or at least allowed only up to physicians' discretion to guarantee the safety of the patients. The possible concomitant use of beta blockers can still be optimized after the optimization period.

Treatment Arm (Cryoablation): Subjects may be prescribed Class I or III AADs for up to 80 days post-ablation procedure at the discretion of the Investigator. Subjects must stop taking all Class I or III AADs before day 81 post-ablation. Use of amiodarone is not permitted.

Anticoagulation requirements for all subjects:

Anticoagulation pre-procedure should be determined based upon the subjects CHA₂DS₂-VASc score.

- a. Oral anticoagulants are required if the subject has had a prior stroke or TIA, or if the subject has a CHA₂DS₂-VASc score ≥ 2 . When anticoagulation is required, subjects must take it for at least 21 days prior to an ablation procedure.
- b. Oral anticoagulants are not required for subjects with nonvalvular AF and a CHA₂DS₂-VASc score of 0 or 1.

Note: TEE must be performed within one day prior to the cryoablation procedure if subjects have a CHA₂DS₂-VASc ≥ 2 and present to the procedure with a sub-therapeutic INR (< 2.0) or if the subject has had a significant interruption of NOACs. A significant interruption of NOACs is defined as any missed dose within 21 days prior to the ablation procedure.

11.3. Subject Consent

Patient informed consent (IC) is defined as a legally effective documented confirmation of a subject's (or their legally authorized representative, US ONLY) voluntary agreement to participate in a particular clinical study after information has been given to the subject on all aspects of the clinical study that are relevant to the subject's decision to participate. This process includes obtaining an Informed Consent Form (ICF) and an Authorization to Use and Disclose Personal Health Information that has been approved by the study center's IRB/EC and signed and dated by the subject (or their legally authorized representative, US ONLY). A subject may only consent after information has been given to the subject on all aspects of the clinical investigation that are relevant to the subject's decision to participate. Informed consent may be given by their legally authorized representative (US ONLY) only if a subject is unable to make the decision to participate in a clinical investigation. In such cases, the subject shall also be informed about the clinical investigation within his/her ability to understand.

Prior to enrolling subjects, the ICF must have been approved by each center's IRB/EC. Each site must also use an Authorization to Use and Disclose Personal Health Information/Research Authorization/other privacy language as required by law. The ICF must be controlled (i.e. versioned and dated) to ensure it is clear which version(s) were approved by the IRB/EC. Any modifications to the sample ICF must be reviewed and approved by Medtronic and the IRB/EC reviewing the application prior to enrolling subjects.

The Investigator must notify the subject (US ONLY: or their legally-authorized representative) of any significant new findings about the study that become available during the course of the study which are pertinent to the safety and well-being of the subject. This could impact a subject's willingness to

participate in the study. If relevant, approval may be requested from subjects to confirm their continued participation.

Prior to initiation of any study-specific procedures, documented IC must be obtained from the subject (or their legally authorized representative, US ONLY). Likewise, privacy or health information protection regulation may require subjects to sign additional forms to authorize centers to submit subject information to the study sponsor. The IC process must be conducted by the principal Investigator or an authorized designee, and the ICF and the Authorization to Use and Disclose Personal Health Information/Research Authorization/other privacy language as required by law must be given to the subject (or their legally authorized representative, US ONLY) in a language he/she is able to read and understand. The process of IC must be conducted without using coercion, undue or improper influence on, or inducement of the subject to participate by the Investigator or other center personnel. The informed consent process shall not waive or appear to waive the subject's legal rights. The language used shall be as non-technical as possible and must be understandable to the subject and the impartial witness, where applicable.

The subject must have ample time and opportunity to read and understand the ICF to inquire about details of the study, and to decide whether or not to participate in the clinical study. All questions about the study should be answered to the satisfaction of the subject. When the subject decides to participate in the clinical study, the ICF and the Authorization to Use and Disclose Personal Health Information/Research Authorization/other privacy language as required by law must be signed and personally dated by the subject (or their legally authorized representative, except in Europe) and either the Investigator or the Investigator's authorized designee, as required by local law. If applicable, witness shall also sign and personally date the consent form to attest that the information in the ICF was accurately explained and clearly understood by the subject, and that IC was freely given.

In Europe, include a personally dated signature by the Principal Investigator or authorized designee responsible for conducting the informed consent process. The Principal Investigator or designee must conduct the informed consent discussion.

A copy of the ICF and the Authorization to Use and Disclose Personal Health Information/Research Authorization/other privacy language as required by law, signed and dated as required by law, must be provided to the subject.

If consent is obtained the same day the subject begins participating in study-related procedures, it must be documented in the subject's case history that consent was obtained prior to participation in any study related procedures. It is best practice for the IC process to be documented in the subject's case history, regardless of circumstance. In the event the subject cannot read and/or write, a witnessed (impartial third party) ICF will be allowed, provided detailed documentation of the process is recorded in the subject's case history and the witness signs and dates the ICF to attest that the information was accurately explained and that informed consent was freely given. In Europe, when a subject cannot read and/or write, an independent witness shall be present throughout the process, the written ICF and any other information shall be read aloud and explained to the prospective subject. The subject should "make his mark" (sign or otherwise physically mark the document so as to indicate consent) on the ICF as well. The ICF should document the method used for communication with the prospective subject and the specific means by which the prospective subject communicated agreement to participate in the study.

The original of the signed ICF and the Authorization to Use and Disclose Personal Health Information/Research Authorization/other privacy language as required by law must be filed in the hospital/clinical chart and/or with the subject's study documents. The ICF and the Authorization to Use and Disclose Personal Health Information/Research Authorization/other privacy language as required by law should also be available for monitoring and auditing. Any Medtronic Field personnel who support the study procedure must be able to review the subject's signed and dated ICF and verify its completeness prior to proceeding with the procedure. In the event the Medtronic Field personnel identify an ICF as being incomplete, the study procedure will not be allowed to occur until the consent of the subject can be adequately and appropriately obtained.

11.4. Randomization and Treatment Assignment

Enrolled subjects are eligible for randomization after all inclusion and none of the exclusion criteria are met and after the baseline QoL questionnaires are completed. Subjects will be randomized in a 1:1 fashion to undergo a cryoablation procedure (treatment arm) or receive AAD therapy (control arm).

See Section 11.5.2 for control arm procedures and Section 11.5.3 for treatment arm procedures.

Subjects will be randomized using an electronic randomization system. The randomization schedule will be stratified by study site to ensure that within each study site randomization is approximately 1:1.

Subjects will be analyzed according to a modified intention-to-treat protocol: subjects who withdraw their informed consent prior to the index cryoablation procedure or initiation of AAD therapy will be excluded from the analysis of the primary safety and efficacy endpoints. Otherwise, the standard intention-to-treat protocol is applied: subjects who receive either therapy, regardless of what it actually is, will be analyzed according to their randomization status. This allows for the protection of the benefits of randomization, while avoiding the problem of attrition and adverse events occurring in the time between randomization and the initiation of treatment, which, due to the practicality of scheduling can be up to 30 days. All randomized subjects should be encouraged to comply with the study procedures until study closure.

11.5. Description of All Study Procedures and Visits

11.5.1. Enrollment & Baseline

The patient is considered a subject enrolled in the study upon completion of the IC process. The date the subject signed the ICF and HIPAA/data protection authorization/or other privacy language where required by law must be documented in the subject's medical records.

All baseline assessments must be performed prior to treatment (cryoablation procedure or initiation of AADs). The following evaluations will be performed after the subject signs the ICF, unless previously performed as part of routine clinical evaluations within the specified windows:

Within 6 months prior to the date the subject signed the Informed Consent Form:

- Trans-thoracic echocardiogram (TTE) for the collection of left atrial size, left ventricular ejection fraction, and mitral valve impairment. A repeat TTE procedure for the purpose of this study is not required if a TTE was performed within 6 months of the date the subject signed the Informed Consent Form and all data are available.

Within 30 days prior to the date the subject signed the Informed Consent Form:

- Physical examination
- CHA2DS2-VASc Score
- 12 lead ECG
- Demographics
- Medical history

After the date the subject signed the Informed Consent Form, but prior to cryoablation procedure or AAD treatment:

Note: The time between randomization and the procedure/AAD initiation must not exceed 30 days. It is recommended that AAD initiation occur within 14 days of randomization. It is recommended that the cryoablation procedure occur within 21 days of randomization.

- Assessment of all factors specified for evaluation under Inclusion Criteria and Exclusion Criteria (Section 10.3 and 10.4), including TTE (required prior to randomization).
- EQ-5D and AFEQT Questionnaires (required prior to randomization)
- Randomization
- Pregnancy screen (required only for female subjects of childbearing potential)
- For this study, a woman of childbearing potential is defined as a premenopausal female capable of becoming pregnant (not sterilized or post-menopausal).
- Review of AF symptoms
- Review of medications to treat atrial arrhythmias and anticoagulation medications
- Transesophageal Echocardiogram (TEE) (treatment arm only)
- TEE must be performed in all subjects who present to the ablation procedure in atrial fibrillation lasting more than 48 hours in duration (or of an unknown duration). However, the TEE is not required if the subject has adequate systemic anticoagulation that has been maintained for at least 3 weeks prior to presenting to the ablation procedure in AF.
- TEE must be performed if subjects have a CHA2DS2- VASc ≥ 2 and present to the procedure with a sub-therapeutic INR (< 2.0) or if the subject has had a significant interruption of NOACs. A significant interruption of NOACs is defined as any missed dose within 21 days prior to the ablation procedure.
- Performance of a TEE in subjects who are in sinus rhythm at the time of ablation or eligible subjects that have been in AF for 48 hours or less prior to AF ablation may be considered but is not mandatory.
- The subject will not proceed with the study ablation procedure and will be exited from the study if a cardiac thrombus is visualized.
- TEE, when required, must be performed within 1 day of the ablation procedure (on the day of or within the day prior to).

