6.3. Minimization of Bias

Selection of subjects, treatment of subjects, and evaluation of study data are potential sources of bias. Methods incorporated in the study design to minimize potential bias include (but are not limited to):

- Subjects will undergo screening to confirm eligibility for enrollment with defined inclusion/exclusion criteria prior to enrollment.
- Subject demographics will be collected at baseline in order to later assess possible characteristics that may influence endpoints.
- All centers and geographies will use the same version of the clinical investigation plan and case report forms.
- All investigational center personnel and Medtronic personnel will be trained on their respective aspects of the study using standardized training materials.
- All investigational center personnel will be trained on and required to follow the CIP.
- An independent Clinical Events Committee (CEC) will be utilized regularly to review and adjudicate reported adverse events and deaths.
- An independent core lab will be utilized to review and adjudicate all ECG recordings from study required 12-lead ECGs and ambulatory monitoring.
- A statistical analysis plan (SAP) will be developed prior to analyzing data. The plan will document all pre-specified analyses and analysis methods.
- Monitoring will be conducted to review adherence to the CIP and perform source data verification per the Monitoring Plan.
- A maximum of 31 treated subjects will be allowed at a single investigational center to ensure an even distribution of total subjects across centers.
- All study investigators in all geographies will be required to comply with 21CFR Part 54, Financial Disclosure by Clinical Investigators.

In summary, potential sources of bias that may be encountered in this clinical study have been considered and minimized by thorough, careful study design.

7. Product Description

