15.1.6. Sample Size

Sample size assumptions are:

- Two-sided chi-squared test
- Alpha=0.05
- AAD 12-month success rate = 45%
- Cryoballoon ablation group 12-month success rate = 69.9%
- Power>90%
- Attrition from randomization to 1 year = 10%

The above assumptions require 87 subjects per arm with data, or 174 total subjects. Adding in 10% attrition brings the overall randomized sample size to 194 for this objective. Note that a log-rank test will be used for the primary efficacy analysis, but the more conservative chi-squared test was used for sample size estimation.

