### 6.2.2.4. Analysis Methods

The probability of a subject achieving success at 12 months (365 days) will be estimated using Kaplan-Meier survival analysis. The standard error will be approximated using Greenwood's formula. A two-sided 95% log-log confidence interval for the probability will be constructed. A log rank test with  $\alpha = 0.05$  will be used to assess whether the failure rate differs between treatment groups.

Day 0 is defined as either the day of the index cryoablation procedure or the day in which AAD drug therapy is initiated. For subjects with treatment failure, the survival date will be set to the date of the treatment failure. For subjects without treatment failure through 12 months, those subjects will be censored at the last study contact date recorded on a CRF, which may include the last study visit, the exit date, or death date. If a subject without a treatment failure is lost to follow-up, the censoring date will be set to the last recorded study visit date. If treatment failure occurs on the day of index treatment, survival time will be set to 0.5 days.

If an occurrence of documented AF/AT/AFL resulted from rhythm monitoring that was initiated at the 12-month visit, then the date of occurrence used in the Kaplan-Meier analysis will be the minimum of 365

days from the cryoballoon ablation procedure/date of AAD initiation, or the actual date of occurrence. This allows counting of all AF/AT/ AFL events found at the 12-month follow-up, even if the follow-up occurred after 365 days post-ablation but still within the visit window. Events found at 12-month visits outside of the window will be censored at the previous follow-up and described in deviation listings.

The survival curves from 0 to 12 months will be presented for both treatment arms.

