### **7.1. Sample Size Determination for Primary Efficacy Objective**

Sample size was estimated using Proc Power in SAS v9.4. The calculation was done to find the number of analyzed subjects necessary to provide a two-sided Pearson’s chi-square test with  $\alpha = 0.05$  and 90% power to detect a difference between two binomial proportions, one of which was 69.9%, and the other 45.9%, under a 1:1 randomization ratio. The two groups’ rates represent the cryoablation and AAD arm 12-month success rates, respectively. The assumed cryoablation arm success rate was what was observed in the STOP AF pivotal trial. The AAD arm success rate estimate, 28 of 61 successes at one year, was observed under similar circumstances in the RAAFT-2 trial (Morillo, et al.).

[figure not shown]
Computed N Total	Actual Power	N Total
	0.901	174

This shows an analytical sample size of 174 subjects is required. However, it was assumed that 10% attrition would occur between enrollment and the 12-month follow-up. Therefore, the necessary enrollment calculated to yield a 90.1% probability of detecting the presumed treatment success difference is 194 subjects.

The sample size estimate attained based on using a chi-square test is conservative compared to the actual number of subjects required using the Kaplan-Meier methods described in 6.2.2, since in the latter case, attrition is partial: data is included for all subjects up until they exit the study, so only subjects who exit prior to day 0 (index ablation or AAD initiation) will provide no information to the analysis.

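### The primary efficacy log-rank test is unadjusted although left atrial diameter and age are known before randomisation: valid, but it gives up a little precision

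*Protocol*

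**What the plan says.** **Baseline data.** Protocol 11.5.1 calls for a "Trans-thoracic echocardiogram (TTE) for the collection of left atrial size, left ventricular ejection fraction, and mitral valve impairment" and places the TTE and the eligibility assessment before randomisation. Left atrial diameter decides an exclusion criterion (10.4) and age an inclusion criterion (10.3). Section 11.4 allows randomisation only "after the baseline QoL questionnaires are completed". For baseline assessments in general, 11.5.1 requires only that they precede treatment. CHA2DS2-VASc falls under that looser rule.

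**Stated use.** Protocol 6.3 lists this among the measures against bias: "Subject demographics will be collected at baseline in order to later assess possible characteristics that may influence endpoints". SAP 6.2.1 summarises baseline characteristics by arm. SAP 6.7 uses age (in quartiles), gender, race and ethnicity as subgroup variables.

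**Primary test.** SAP 6.2.2.4 plans Kaplan-Meier estimates and a log-rank test at 0.05 that "will be used to assess whether the failure rate differs between treatment groups". Protocol 15.1.5 plans the same. Neither names a covariate.

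**Sizing.** Protocol 15.1.6 uses a "Two-sided chi-squared test" with "Cryoballoon ablation group 12-month success rate = 69.9" and "AAD 12-month success rate = 45" (both per cent). SAP 7.1 uses two proportions, "one of which was 69.9%, and the other 45.9%, under a 1:1 randomization ratio".

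**The concern.** If left atrial diameter and age predict recurrence, an unadjusted test treats that predictable variation as noise. With about 105 subjects per arm and randomisation stratified only by site, the arms can differ by chance on these factors, and the difference goes straight into the observed result. The trial is unblinded and analysed by sponsor statisticians, so an adjustment chosen after an imbalance has been seen would carry little weight. The covariates are already collected, so what is at stake is some precision and the chance to settle the adjustment in advance.

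**Working it through.** **1. Reproduce the plan's figure.** For two proportions, two-sided 0.05 and 90% power:

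n per arm = [1.96·√(2·p̄·(1−p̄)) + 1.2816·√(p1(1−p1) + p2(1−p2))]² / (p1−p2)²

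With 0.699 and 0.459, p̄ = 0.579 and n = (1.368 + 0.868)² / 0.0576 = 86.8, so 87 per arm or 174 in total. Power is 0.9005, and 174/0.9 rounds up to 194. This matches SAP 7.1. The protocol's 45% gives 81 per arm (162, or 180 after attrition), so its stated 87 needs the SAP's 45.9%. The two rates should be reconciled.

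**2. Power of the planned test at the actual size.** The design hazard ratio is ln 0.699 / ln 0.459 = 0.460, a log HR of −0.777.
- With 189 analysable (210 less 10%), events = 94.5 × (0.301 + 0.541) = 79.6. Schoenfeld power = Φ(0.777·√79.6/2 − 1.96) = 93.4%.
- With all 210 followed, events = 88.4 and power is 95.5%.
- Partial follow-up of dropouts puts the planned power at about 94%.

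**3. Effect of adjustment.** Prognostic strength is not in the documents. *Assumption:* one standard normal baseline score with log HR per SD of 0, 0.2, 0.4 or 0.6 (HR 1.00, 1.22, 1.49, 1.82). The simulation used 105 per arm, 10% dropout, failures after day 90, arm success rates held at the stated values and 4,000 trials per scenario. The adjusted test regresses each subject's log-rank contribution on the covariate within arm, subtracts the predicted part and standardises by the reduced variance. The 65.9% scenario is an assumption: a difference of 20 points in place of 24.

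| Log HR per SD | 69.9% vs 45.9%: unadjusted → adjusted | Gain (points) | 65.9% vs 45.9%: unadjusted → adjusted | Gain (points) |
|---|---|---|---|---|
| 0 | 94.2 → 94.3 | 0.1 | 82.3 → 82.6 | 0.3 |
| 0.2 | 93.5 → 94.0 | 0.5 | 82.9 → 83.6 | 0.7 |
| 0.4 | 94.0 → 95.0 | 1.0 | 83.4 → 86.2 | 2.8 |
| 0.6 | 94.5 → 96.3 | 1.8 | 82.6 → 88.1 | 5.5 |

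The Monte Carlo standard error of each power is about 0.4 points at 94% (√(0.94·0.06/4000)) and 0.6 points at 83%. Further runs of these designs gave gains of 0.6, 1.2 and 2.6 points at the design rates and 0.4, 2.8 and 4.6 points at 65.9%, for strengths 0.2, 0.4 and 0.6. A covariate-adjusted Cox model with 189 complete subjects gave 92.9 → 93.0, 92.8 → 94.5 and 93.4 → 96.1.

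**4. Type I error.** The unadjusted log-rank test rejected in 5.1% to 5.4% of null trials, and the adjusted log-rank test in 4.7% to 5.2%. Both agree with 5%.

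**5. Size of a chance imbalance.** The standardised mean difference between arms has SD √(2/105) = 0.138, so a 1-in-20 imbalance is 1.96 × 0.138 = 0.27 SD. At log HR 0.4 it moves the log HR by about 0.4 × 0.27 = 0.11, which is 0.11/0.777 = 14% of the design effect. At 0.2 and 0.6 the shares are 7% and 21%. The shift can favour either arm.

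**The case against.** The strongest reply is that nothing here is an error. Randomisation protects the unadjusted log-rank test, and chance imbalance is already part of its null distribution. A reader might infer from the imbalance argument that the p-value is biased or the test invalid. Step 4 does not support that, and the objection stands in full on this point.

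A reader might also infer that the trial is underpowered, or that adjustment would save subjects. Neither follows. Efficacy power already exceeds 90%, and SAP 6.8 and 7.2 show that the single-arm safety test sets the 210 (94/0.9 rounds up to 105 per arm). The margin over 90% does depend on an AAD rate taken from 28 of 61 subjects (0.459 ± 1.96·√(0.459·0.541/61), about 33% to 58%), so a smaller true difference is plausible. That is where adjustment helps most.

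The gain rests on assumed prognostic strength, and the left atrial range is cut off at 5.0 cm by eligibility. The simulation above also leaves out acute procedural failure on day 0. Adding 5% such failures at the design rates left the gain at about 0.5 to 2.5 points.

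Two more inferences go too far. One is that every baseline value precedes randomisation: this is shown for the TTE, the eligibility factors and the questionnaires, but not for CHA2DS2-VASc. The other is that baseline data go unused, or that no adjusted analysis exists anywhere. Age is a subgroup variable, and parts of the SAP are redacted.

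**Conclusion.** In the readable text the primary efficacy test is unadjusted, although two plausible prognostic factors are fixed before randomisation. This is a modest loss of precision and not a validity defect. Over assumed log HRs per SD of 0.2 to 0.6, adjustment is worth about 0.5 to 3 points of power at the design rates and about 0.5 to 5 points at 65.9% vs 45.9%. There is no material loss when the covariate is not prognostic. The sizes rest on that assumed range, proportional hazards after day 90 and 10% dropout. The case for acting now is pre-specification as much as power.

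**What to change.** Before outcome data are reviewed:
- In SAP 6.2.2.4 and Protocol 15.1.5, make the primary test a covariate-adjusted log-rank test at two-sided 0.05, with continuous left atrial diameter and age (as calculated in SAP 6.7) named as covariates. Align SAP 6.2.2.3 and Protocol 15.1.3, which also name the log-rank test.
- Keep the Kaplan-Meier estimates and intervals, and report the unadjusted log-rank test as a sensitivity analysis.
- Use the same adjusted test in the tipping-point steps of SAP 6.4.1, which refer back to 6.2.2.4.
- Use CHA2DS2-VASc only where it was recorded before randomisation.
- State a rule for a missing covariate that ignores treatment arm, such as the overall mean, so that no subject is dropped.

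**Cost.** No new data, only SAP text and a little programming and validation. Protocol section 15 requires an amendment if a principal feature changes, and the primary test may count as one. Section 17.6 then brings in sponsor, ethics and regulatory approvals. If the sponsor does not want that, leave the primary log-rank test as it is and pre-specify the adjusted log-rank test with these named covariates as a supportive analysis in a new SAP version, which SAP 6.8 allows.
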